# 7.3.4 Vital Signs and Physical Examination

Vital signs (blood pressure, heart rate, respiratory rate, body temperature) will be assessed at the following time-points: at screening, prior and – in case IMP was injected – 30-60 minutes after the end of the injection at 3-monthly ( $\pm 2$  weeks) visits, and prior and – in case IMP was injected – 30-60 minutes after the end of the injection at the completion visit. During surgical procedures vital signs will be assessed before, during and at the first post-operative day.

A physical examination needs to be performed at screening, once every 6 months and at study completion.

# 7.3.5 Other Relevant Safety Information

# Post study related safety reports:

Any ADR (i.e., any AE with a suspected causal relationship to the IMP) that occurs after the completion of the study should be reported by the Investigator. The usual procedure for reporting post-marketing safety information should be followed, but relation to the clinical study should be stated on the report.

If a patient dies within 4 weeks after the last IMP administration, this should be reported as well, without being considered treatment-related or not.

# Overdose, interaction, abuse, misuse, medication error and lack of efficacy:

The following safety relevant information should be reported as an AE or, if the reaction fulfils one of the criteria for seriousness, as a SAE.

# Drug overdose:

An overdose is a deliberate or inadvertent administration of a treatment at a dose higher than that specified in the protocol, and higher than the known therapeutic dose and of clinical relevance. The reaction must be clearly identified as an overdose.

## Interaction:

A drug interaction is a situation in which a substance/medicinal product affects the activity of an IMP, i.e., the effects are increased or decreased, or they produce an effect that none of the products exhibits on its own. The reaction must be clearly identified as drug interaction.

# Misuse:

Misuse is the deliberate administration or use of the medicinal product outside its described indication or outside the current state of the art medical practice (off-label-use). The reaction must be clearly identified as misuse.

## Medication error:

Medication error involves the inadvertent administration or unintended use of a medicinal product which may be caused by the naming, presentation of pharmaceutical form/packaging, instructions for use/labelling. The reaction must be clearly identified as a medication error.

# 7.4 Other Assessments

# 7.4.1.1 Recovery investigation (optional)

A recovery investigation is recommended to be performed with the first *Human-cl rhFVIII* administration, or within the first three months after treatment start with *Human-cl rhFVIII*, in any case in a non-bleeding patient. A dose of 40 IU FVIII/kg BW will be administered and the *in vivo* recovery will be calculated from the FVIII levels before infusion and the peak level obtained from the 15 min and 1 hour post-infusion samples. Recovery investigations are recommended to be repeated approximately every 6 months.

## 7.4.1.2 RNA Expression Analysis (Optional)

RNA expression analysis will optionally be performed in order to provide an understanding of the transcript activity of the genes involved in immune responses that may be responsible for FVIII inhibitor formation in patients receiving exogenous FVIII. RNA expression analysis will also be optionally performed on patients undergoing ITI to provide information on the transcript activity of genes involved in immune tolerance. The analysis will be carried out using a customised PAXgene protocol in which RNA samples will be obtained by using commercially available PAXgene RNA blood collection tubes and customised microfuge tubes. This customised approach has previously been used in both a paediatric and animal study where samples volumes are limited (6),(7). The full protocol for this sub-study can be found in Appendix 2.

# 7.4.1.3 Immunogenotyping (Partly Optional)

Immunogenotyping will be performed in order to investigate genetic factors that might influence development of FVIII inhibitors. It will include analysis of FVIII gene mutations, HLA-typing, immune response gene profiling and FVIII ethnic haplotype analysis. FVIII mutation analysis is a required assessment, whereas HLA-typing, immune response gene profiling and FVIII ethnic haplotype are optional. Blood samples required for this analysis can be obtained at any time during the study, but it is recommended that they be obtained at the same time as the samples for scheduled study visits.

# 7.4.1.4 In vitro immunogenicity of FVIII products (optional)

Immunogenicity of *Human-cl rhFVIII* will be assessed by culturing peripheral blood monocyte cells (PBMC) from the patients (including a positive control) with *Human-cl rhFVIII*. The nature of T cell response will be assessed by analysing cytokine expression (measured in a multiplex format) and T cell proliferation. Cytokines analysed will include IL-2, TNF $\alpha$ , IFN $\gamma$ , IL-5, IL-6, IL-10, and IL-17 (TGF $\beta$  may also be included in an ELISA format).

## 7.5 Appropriateness of Measurements

All measurements used for the assessment of the immunogenicity, safety, and efficacy of *Human-cl rhFVIII* are in compliance with the requirements set up in the CHMP "Guideline on the clinical investigation of recombinant and human plasma-derived factor VIII products" (EMA/CHMP/BPWP/144533/2009) (5).

Amended Study Protocol	CONFIDENTIAL	Version 05
No. GENA-05		01-Feb-2018

All FVIII inhibitor and FVIII plasma level samples obtained in the course of this study will be evaluated by an accredited central laboratory using validated methods and assays.

If clinically indicated, FVIII and inhibitor testing can additionally be performed in the local laboratory. The results obtained locally will be recorded in the CRFs.

# 8 DATA HANDLING AND RECORD KEEPING

## 8.1 Documentation of Data

## 8.1.1 Source Data and Records

Source data are defined as all the information related to clinical findings, observations, or other activities in the study, written down in original records or certified copies of original records allowing reconstruction and evaluation of the clinical study.

The Investigator will maintain adequate source records (e.g., case histories or patient files for each patient enrolled). Source records should be preserved for the maximum period of time required by local regulations.

For each patient enrolled, the Investigator will indicate in the source record(s) that the patient participates in this study.

All data entered in the CRF must be supported by source data in the patient records with the exceptions listed in Section 8.1.2.

The Investigator will permit study-related monitoring, audit(s), Independent Ethics Committee [IEC]/ Institutional Review Board [IRB] review(s) and regulatory inspection(s), by providing direct access to source data/records.

The Investigator may authorise site staff (e.g., sub-Investigators, nurses) to enter study data into the CRF. This must be documented in the "Delegation of Authority Log", filled in and signed by the Investigator responsible.

# 8.1.2 Case Report Forms

For each patient enrolled, a CRF will be completed and signed by the Investigator or an authorised Co-Investigator. All forms will be filled out using an indelible pen, and must be legible.

# 8.1.3 Changes to Case Report Form Data

Errors occurring in CRFs will be crossed out without obscuring the original entry, the correction will be written alongside the initial entry, and the change will be initialled and dated by the Investigator or authorised study site personnel. When changes to CRF data are necessary following removal of the original CRF from the study site, any such changes will be documented on data clarification / resolution forms, which will be submitted to the Investigator for signature.

If reason for the change is not obvious, then a reason should be given. The Principal Investigator must, as a minimum, sign the final CRF page to attest the accuracy and completeness of all the data. Once the data have been entered onto the database, they will be checked and any discrepancies will be raised and returned to the Investigator for resolution. Data will be monitored and tabulated in accordance with the Data Management Plan.

## 8.2 Information of Investigators

An Investigator's Brochure will be handed out to the Investigator before the start of the study. This Brochure contains all information in the Sponsor's possession necessary for the Investigator to be fully and accurately informed about the safety of the IMP under evaluation and the respective benefit-risk ratio.

The Investigator's Brochure will be updated by the Sponsor at regular intervals and in case new information concerning the IMP becomes available.

The Investigators will be informed about the methods for rating relevant study outcomes and for completing CRFs in order to reduce discrepancies between participating Investigators and study sites.

The Investigator will be kept informed of important data that relate to the safe use of the IMP as the study proceeds.

# 8.4 Investigator's Site File

At each study site, the Investigator is responsible for maintaining all records to enable the conduct of the study to be fully documented. Essential documents as required by GCP guidelines and regulations (e.g., copies of the protocol, study approval letters, all original informed consent forms, site copies of all CRFs, drug dispensing and accountability logs, correspondence pertaining to the study, etc.) should be filed accurately and kept by the Investigator for the maximum period of time required by local regulations.

The Investigator is responsible for maintaining a confidential patient identification code list, which provides the unique link between named source records and CRF data for the Sponsor. The Investigator must arrange for the retention of this confidential list for the maximum period of time required by local regulations.

No study document should be destroyed without prior written agreement between the Investigator and the Sponsor. Should the Investigator elect to assign the study documents to another party, or move them to another location, the Sponsor must be notified in writing.

# 8.5 **Provision of Additional Information**

On request, the Investigator will supply the Sponsor with additional data relating to the study, or copies of relevant source records, ensuring that the patient's confidentiality is maintained. This is particularly important when CRFs are illegible or when errors in data transcription are encountered. In case of particular issues or governmental queries, it is also necessary to have access to the complete study records, provided that the patient's confidentiality is protected in accordance with applicable regulations.

# 8.6 Independent Data Monitoring Committee

Inhibitor and safety data this study will be monitored at specified intervals by an Independent Data Monitoring Committee (IDMC). The IDMC will be composed of recognised experts in the field of haemophilia who are not actively recruiting patients. The study Sponsor will formally convene the IDMC at least once per year until completion of the trial program. Adhoc meetings will be held, if needed.

# 9 STATISTICAL METHODS AND SAMPLE SIZE

The statistical analysis will be delegated under an agreement of transfer of responsibilities to an external CRO. All Octapharma procedures and policies have to be met by this CRO. Discrepancies or exceptions are to be approved by the Sponsor's Manager of Biometrics.

# 9.1 Determination of Sample Size

No inferential analysis involving formal testing is planned in this non-controlled study. Consequently, no formal sample size estimation was performed, but the sample size was chosen to satisfy current CHMP recommendations.

Amended Study Protocol	CONFIDENTIAL	Version 05
No. GENA-05		01-Feb-2018

According to the CHMP "Guideline on the Clinical Investigation of Recombinant and Human Plasma-Derived Factor VIII Products" (EMA/CHMP/BPWP/144533/2009) (5), a minimum of 50 PUPs evaluated for efficacy and safety during at least 50 ED, connected with a post-approval commitment to follow up at least 100 PUPs (50 from efficacy/safety trial and 50 new) for a minimum of 100 ED, is necessary.

# 9.2 Statistical Analysis

A formal statistical analysis plan (SAP) describing all details of the analyses to be performed will be prepared by the study statistician and approved by the Sponsor prior to the start of the study.

The statistical analysis of the endpoints is to be understood in the exploratory sense. No confirmatory hypothesis testing is planned.

# 9.2.1 Population for Analysis

For the analysis of this study, the following populations will be considered:

- Safety analysis population: All subjects who received at least one dose of *Human-cl rhFVIII*;
- Intent to Treat (ITT) analysis population: All subjects in the safety analysis population for whom any data was collected post treatment with *Human-cl rhFVIII*;
- Efficacy: Per Protocol (PP) analysis population: All subjects in the ITT analysis population who completed the trial without significantly violating the inclusion/exclusion criteria or other aspects of the protocol considered to potentially affect the efficacy results. Especially the following subjects will be excluded from this population:
  - Subjects who violate the following inclusion criteria:
    - severe Haemophilia A (FVIII:C <1%; historical value as documented in subject records),
    - No previous treatment with FVIII concentrates or other blood products containing FVIII
  - Subjects who fulfil the following exclusion criteria:
    - other coagulation disorder than Haemophilia A
    - severe liver or kidney disease (ALT and AST levels >5 times of ULN, creatinine >120 μmol/L),
    - concomitant treatment with any systemic immunosuppressive drug
    - subjects who use concomitant medication that may confound study results, like e.g. alpha-interferon or prednisone
  - Subjects with significant non-compliances with the protocol such as non-compliance to complete the diary in a proper manner or more than 30% of haemostatic efficacy assessments missing.
  - A minimum of inhibitor tests (baseline, after 1-4 EDs, 10-15 EDs and 50 EDs) is available
  - Subjects with dosing or treatment errors like e.g. the use of other FVIII products (except for emergencies as mentioned above) or several *unexplained* and significant deviations from the recommended dose regimen.
  - Patients with less than 100 days of exposure to *Human-cl rhFVIII*.

- Subpopulations of the ITT populations will be
  - Subjects of each ethnic group
  - Subjects with ITI treatment
  - Subjects with breakthrough bleedings, if appropriate
  - Subjects with surgical interventions, if appropriate
  - Subpopulations especially for inhibitor incidence analysis:
    - Subjects with different FVIII gene mutations
    - Subjects with/without family history of inhibitors
    - Subjects by classes of EDs prior to inhibitor generation
    - Subjects by reason for treatment prior to inhibitor generation
    - Subjects by intensity of treatment with/without peak treatment moments before inhibitor appearance (peak treatment moments defined as ≥3 subsequent days with FVIII dosing)
    - Subjects by classes of prophylactic treatment (amount and frequency)
- Population of subjects on prophylactic treatment schedule (PROPH): All subjects in the ITT population who have at least one prophylactic treatment
- Per-protocol population of subjects on prophylactic treatment schedules (PROPH-PP): All subjects in the PP population who have at least 100 EDs of treatment and who have no significant dosing or treatment errors, like e.g. unexplained interruptions of the prophylaxis with *Human-cl rhFVIII*
- Population of bleedings (BLEED): All documented bleeds except those occurring during and after surgery of subjects in the ITT population for which
  - any amount of treatment with *Human-cl rhFVIII* is documented and which
  - start between first BE treated with *Human-cl rhFVIII* and the completion visit.
- Population of bleedings per protocol (BLEED-PP): All documented bleeds in the BLEED population of subjects in the PP population.
- Surgery population (SURG): All documented surgical interventions of subjects in the ITT population for which
  - any amount of *Human-cl rhFVIII* prior to, during or after the surgery is documented and
  - no other FVIII concentrate is documented within 24 hours prior to surgery.
- Surgery per-protocol population (SURG-PP): All documented surgical interventions of subjects in the PP population for which
  - any amount of *Human-cl rhFVIII* prior to, during or after the surgery is documented and
  - no other FVIII concentrate is documented within 72 hours prior to, during or after the surgery (until resuming regular prophylactic treatment or until discharge from hospital in case of a subject with on-demand treatment).

The subject disposition, i.e. the identification of significant violations to consider for the PP populations and the assignment of each subject, bleeding and surgery to these analysis populations, will be the joined decision of the trial statistician and the responsible medical expert prior to database lock.

Amended Study Protocol	CONFIDENTIAL	Version 05
No. GENA-05		01-Feb-2018

The ITT population is considered to be the most relevant for analysis of immunogenicity data; the PROPH population is considered to be the most relevant for analysis of efficacy data on prophylaxis; the BLEED population is considered to be the most relevant for analysis of efficacy data on bleedings and the SURG population is considered to be the most relevant for analysis of efficacy data on surgeries. To evaluate the robustness of the study results, efficacy analyses will also be done on basis of the respective PP population.

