3.4 Assessment of Objectives

3.4.1 Immunogenicity

The *primary objective* is to investigate the immunogenicity of Human-cl rhFVIII.

The *primary endpoint* is the incidence of inhibitors within the observation period. For one patient an inhibitor is assessed to be positive if the modified Bethesda assay (Nijmegen modification) results in a titer ≥ 0.6 BU at any time point during the observation period.

Inhibitor activity will be determined centrally at the following time points: At baseline (Screening Visit), every 3-4 EDs until ED 20, every 10-12 EDs or every 3 months \pm 2 weeks after ED 20 (whichever comes first), at study completion; at any time in the case of a suspicion of inhibitor development.

In case of a positive inhibitor result, an inhibitor re-testing using a second separately drawn sample should be performed centrally; the result of the second sample will be taken as the final result for the time point. Low titre inhibitors will be defined as ≥ 0.6 to < 5 BU, high-titre inhibitors will be defined as ≥ 5 BU.

Patients who develop a non-transient inhibitor will have an option to start ITI treatment. Patients developing inhibitors and not starting ITI within one year after inhibitor detection will be

withdrawn from the study. Inhibitors that 'disappear' without any clinical signs or symptoms, where no FVIII dosing increase was required, and that turn back to <0.6 BU within a period of 6 months after first detection are regarded as "transient". Patients who develop such a transient inhibitor will continue regular treatment within the study until they have reached ED 100 or a maximum period of 5 years.

Definition of inhibitor confirmation and time to inhibitor occurrence:

Occurrence of inhibitors:

For these definitions inhibitor titres determined in the central laboratory are considered.

(I1) FVIII:C high titre inhibitor occurrence is confirmed, if

inhibitor level ≥ 5 BU at one time point $t_{1,H}$ and

- inhibitor level confirmed to be ≥ 5 BU at a subsequent* time

point $t_{2,H}$ or

- retest of sample from *any* time point $t_{3,H}$ ($=t_{1,H}, t_{2,H}$ or later) confirmed to be ≥ 5 BU.

* 'Subsequent' in the context of this document always means 'at a later time point' or 'in a later sample', but not necessarily the immediate consecutive visit or sample.

(I2) FVIII:C Inhibitor occurrence in a patient is confirmed, if

- a high titre inhibitor is confirmed according to (I1)

or if

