4.2 Sample Size

100 evaluable previously untreated patients (PUPs) will be enrolled in this study.

No inferential analysis involving formal testing is planned in this non-controlled study.

Consequently, no formal sample size estimation was performed, but the sample size was chosen to satisfy CHMP recommendations.

According to the CHMP “Guideline on the Clinical Investigation of Recombinant and Human Plasma-Derived Factor VIII Products” (EMA/CHMP/BPWP/144533/2009) [1], a minimum of 50 PUPs evaluated for efficacy and safety during at least 50 EDs, connected with a post-approval commitment to follow up at least 100 PUPs (50 from efficacy/safety trial and 50 new) for a minimum of 100 ED, is necessary.

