4.4 Study Assessments

For assessments directly related to the evaluation of the primary and secondary endpoints, please refer to section 3.4 (Assessment of Objectives).

The following parameters will be assessed to allow a meaningful characterisation of the study population and to collect background information required for medical evaluation of study events:

- Subject demographics and baseline characteristics:
including ethnicity, age, height, weight, family history of haemophilia and inhibitors against FVIII.
- F8 gene mutation analysis including null/non-null specification
- Immunogenotyping
(HLA-typing, immune response gene profiling, F8 ethnic haplotype determination)
- RNA expression analysis
- FVIII level and recovery determination
- Half-life determination for patients under ITI treatment

- Medical History
- Concomitant Medication will be recorded throughout the trial
- Physical examinations will be performed at screening, at six monthly visits and at the completion visit.

5 **STUDY POPULATIONS**

5.1 **Subject Disposition**

For the analysis of this study the following populations will be considered:

- **Safety analysis population**: All subjects who received at least one dose of *Human-cl rhFVIII*
- **Intent to Treat (ITT) analysis population**: All subjects in the safety analysis population for whom any data was collected post treatment with *Human-cl rhFVIII*

Subpopulations of the ITT population will be

- Subjects of each ethnic group
 - Subjects with ITI treatment
 - Subjects with breakthrough bleedings, if appropriate
 - Subjects with surgical interventions, if appropriate
 - Subpopulations especially for inhibitor incidence analysis:
 - Subjects with different F8 gene mutations
 - Subjects with/without family history of inhibitors
 - Subjects by classes of EDs prior to inhibitor generation (1-5, 6-10, 11-20, 21-50, > 50)
 - Subject's age at first exposure (< 1, 1-6, > 6-12, > 12 months)
 - Subjects by reason for treatment prior to inhibitor generation
 - Subjects by intensity of treatment with/without peak treatment moments before inhibitor appearance (peak treatment moments defined as
 - ≥ 3 subsequent days with FVIII dosing, and/or
 - at least one day with prophylactic doses of > 50 IU FVIII /kg BW)
 - ED50 sub-population: Patients in the ITT population with at least 50 EDs of treatment with *Human-cl rhFVIII*
 - ED20 sub-population: Patients in the ITT population with at least 20 EDs of treatment with *Human-cl rhFVIII*.

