8 EVALUATION OF TREATMENT COMPLIANCE AND EXPOSURE

Prophylaxis, ITI treatment and treatment of Bes and surgeries: The following will be tabulated and/or summarized:

- Reason for Administration
- Number of Injections
- First dose, last dose, number of Exposure Days
- Total Dose (IU)
- Dose (IU FVIII/kg BW)

Furthermore, the *Human-cl rhFVIII* batches used will be listed for both assays with their potencies in the listings for doses.

9 **EVALUATION OF TREATMENT EFFICACY**

9.1 **Immunogenicity**

All recorded determinations of inhibitors against FVIII will be listed. The absolute number and cumulative incidence of inhibitors (inhibitor titre ≥ 0.6 , < 5 BU and ≥ 5 BU respectively) will be presented in total, and as percentage of the analysis population, with a 95% confidence interval. If justified by the number of events, the time period until the first inhibitor activity will be tabulated and displayed graphically by means of a Kaplan-Meier plot of percentages without inhibitor versus cumulative EDs until appearance of inhibitor, and a logistic regression analysis of incidence rates of FVIII inhibitor development will be performed (prognostic factors: family history of inhibitor, family history of hemophilia, weight, mean dose/ED, age, F8 gene mutation defect (including null/non-null, high/low risk mutation analysis), number of EDs before inhibitor development, age at first treatment, intensity of treatment (number of peak treatment moments), country ethnicity, center).

In addition, number of EDs until inhibitor development will be shown in life-table lists showing the incidence of inhibitors per interval of 5 EDs; a Cox regression will analyse the ED to inhibitor data for the impact of possible prognostic variables (same list as for logistic regression analysis above).

The incidence of low and high titre FVIII inhibitors will also be presented grouped by ethnicity and F8 gene mutations categorized as null/non-null and as high/low risk, incl. results of the immunogenotyping sub-study. For the combined presentation of subgroup results, Forest plots will be provided.

The number of EDs before inhibitor development will be tabulated for each patient with FVIII inhibitors.

RNA expression analysis data and Antitope Ltd. sub-study data will not be analysed under this SAP.

9.2 **Prophylaxis (Prevention of Bleeding episodes)**

The following will be presented following the manners of representation described in section 6:

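### The SAP's own definition of 'subsequent' turns almost any three dosing days into a peak treatment moment, so the treatment-intensity factor would mainly reflect the number of exposure days

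*Protocol*

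**What the plan says.** SAP 3.4.1, in a note to the high-titre confirmation rule I1, fixes the meaning of 'subsequent' for the whole SAP: the word "in the context of this document always means 'at a later time point' or 'in a later sample". The same note then adds a qualification, namely that the occasion meant is "but not necessarily the immediate consecutive visit or sample".

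SAP 5.1 lists among the subpopulations for inhibitor incidence "Subjects by intensity of treatment with/without peak treatment moments before inhibitor appearance". It gives two criteria for a peak treatment moment. The first rests on dosing days: "≥ 3 subsequent days with FVIII dosing, and/or". The alternative rests on dose and asks for "at least one day with prophylactic doses of > 50 IU FVIII /kg BW". It makes no exception to the earlier note.

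Protocol 9.2.1 has only the first criterion ("peak treatment moments defined as ≥3 subsequent days with FVIII dosing") and does not define 'subsequent'.

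SAP 9.1 enters the factor in the logistic regression as "intensity of treatment (number of peak treatment moments" and uses the same covariate list for the Cox regression. That list also contains the number of EDs before inhibitor development. SAP section 13 uses intensity in Table 14.2.1.1 (incidence by subgroup), Tables 14.2.2.1 to 14.2.2.4 (time and EDs to inhibitor), and Tables 14.2.5 and 14.2.6 (the two regressions).

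**The concern.** A peak treatment moment is meant to mark a burst of intensive exposure. If 'subsequent' carries the meaning the SAP assigns to it, the days need not adjoin, and ordinary once-weekly or every-other-day prophylaxis qualifies as soon as the third dose is given. The yes/no subgroup then has almost nobody on one side, and the count measures how long a patient has been treated rather than how intensively.

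The literal reading has support elsewhere in the SAP. Rule I2 asks for positive results at three subsequent time points, where non-adjacent samples are plainly intended. The word also just means later for confirmatory titres (3.4.1), for repeat bleeds at one site (3.4.2) and for ITI determinations (6.4.2). The peak-moment definition needs the opposite meaning. Two programmers could therefore produce very different intensity tables from the same text.

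**Working it through.** There is no figure in the plan to reproduce; "no formal sample size estimation was performed, but the sample size was chosen to satisfy CHMP recommendations", and no power or alpha bears on this point. The check applies the definition to dosing calendars.

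**Inputs from the documents**
- Literal meaning of 'subsequent': later, not necessarily consecutive (SAP 3.4.1).
- Threshold: at least 3 dosing days (SAP 5.1, Protocol 9.2.1).
- Scheduled inhibitor tests: every 3-4 EDs until ED 20, plus tests at any time on suspicion (SAP 3.4.1).
- EDs to inhibitor: counted from ED 1 to the day before the first positive titre (SAP 3.4.1, rule I4).
- Regimens named as examples: once, twice or three times weekly, or every other day (Protocol 5.4).

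**Assumed for illustration:** calendars of 20 EDs on each regimen; one calendar of 17 weekly doses plus a three-day bleed treatment (17 + 3 = 20 EDs); inhibitors found after 2 or 3 EDs.

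**Step 1: when the literal criterion is met.** The third dosing day falls on day 5 with every-other-day dosing (days 1, 3, 5) and on day 15 with weekly dosing (days 1, 8, 15). A first scheduled test after 3-4 EDs has at least 3 EDs before it, so an inhibitor detected on schedule belongs to a patient who already qualifies.

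**Step 2: the yes/no split and the count** (first criterion only).

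| Calendar | EDs | Literal: with? | Consecutive: with? | Consecutive: runs of at least 3 days |
|---|---|---|---|---|
| Once weekly | 20 | yes | no | 0 |
| Twice weekly | 20 | yes | no | 0 |
| Three times weekly | 20 | yes | no | 0 |
| Every other day | 20 | yes | no | 0 |
| Weekly plus one 3-day bleed treatment | 20 | yes | yes | 1 |
| Inhibitor after 3 weekly EDs | 3 | yes | no | 0 |
| Inhibitor after 2 EDs | 2 | no | no | 0 |

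**Step 3: the literal count for n EDs.** Neither document says how moments are counted. Three possible rules at n = 20:
- non-overlapping triples: floor(n/3) = floor(20/3) = 6
- sliding window: n − 2 = 18
- all triples: n(n − 1)(n − 2)/6 = 20 × 19 × 18/6 = 1140

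Each is a function of n alone, so all five 20-ED calendars give the same value. Under the literal reading this criterion adds little to a model that already contains the number of EDs.

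**Step 4: the dose criterion.** The alternative of a prophylactic dose above 50 IU/kg can only move patients from 'without' to 'with', so it does not restore the split. It can add to the regression count, so that count need not be a pure function of EDs.

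**The case against.** The strongest reply is that the note was written for laboratory samples. It is attached to an inhibitor-confirmation rule, and its wording concerns time points, visits and samples, not dosing days. The term being defined is a *peak* treatment *moment*, under the label of treatment intensity; doses spread over weeks are neither. A sensible analyst may well program consecutive days, and nothing in the documents shows that the literal version was used. This stands: the risk is ambiguity, not demonstrated error. It does not remove the conflict, because the note says the meaning always applies in the document and itself contrasts 'subsequent' with 'consecutive'.

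The analyses are also exploratory (SAP 6.4), the logistic regression is conditional on enough events, and intensity is one of about a dozen prognostic factors. That stands too, and it limits the severity.

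A reader might go further and infer that the factor cannot separate patients at all, that the 'without' group must show 0% inhibitors by construction, or that the Protocol contradicts itself. The documents do not support these:
- Tests on suspicion are allowed at any time, and the per-protocol test minimum in Protocol 9.2.1 includes a test after 1-4 EDs. An inhibitor can be found before 3 EDs, and that patient is 'without' on the first criterion. Early leavers can be too.
- The count does vary between patients, although under the literal reading mainly with EDs.
- The SAP note governs only the SAP. In the Protocol the word is undefined and reads naturally as a run of days.

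**Conclusion.** The conflict lies inside the SAP, between the note in 3.4.1 and the definition in 5.1. Applied literally, nearly all patients are 'with' peak treatment moments, and the regression covariate mainly duplicates the number of EDs. Applied as consecutive days, the definition separates regular prophylaxis (0 in each example) from a three-day bleed treatment (1).

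The size of the effect depends on which reading is programmed and on dosing histories that the documents do not give; the calendars above are illustrations. It would be tempting to quote about 33 moments per patient at 100 EDs (floor(100/3) = 33), but that rests on a counting rule found in neither document; a sliding window would give 100 − 2 = 98.

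The effect is confined to the intensity subgroup, Tables 14.2.1.1 and 14.2.2.1 to 14.2.2.4, and the logistic and Cox models. The overall inhibitor incidence and its 95% confidence interval do not use the definition. Minor severity.

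**What to change.** 1. In SAP 5.1, word the first criterion as *at least 3 consecutive calendar days with FVIII dosing*.
2. In SAP 3.4.1, limit the note on 'subsequent' to the inhibitor sampling rules.
3. In SAP 9.1, state that one uninterrupted run counts as one peak treatment moment, and say how a day that qualifies only on the dose criterion enters the count.
4. Change Protocol 9.2.1 to the same wording only as a conforming edit.

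The cost is a few words in the SAP and one in the Protocol. No new data are needed, because dates and doses of all injections are already recorded.
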